mg) will be prepped for electron microscopy for future analysis of morphology (mitochondrial size, content, ragged muscle fiber analysis) (66). Remaining muscle will be frozen for later analysis of intracellular atorvastatin concentration (both the acid and lactone forms) (67), ubiquinone (co-enzyme Q10) (68, 69), and potential future gene array, metabolomics, or proteomics analysis. An in-vivo assessment of mitochondrial function using NIRS will determine muscle oxygen consumption (mVO₂) and the recovery kinetics will be determined during a series of repeated arterial occlusions following maximal knee extension. The mVO₂ data are fit to a mono-exponential function to calculate the rate constant, which is directly related to the mitochondrial respiratory capacity. (46). The protein and mRNA for key transcriptional factors controlling mitochondrial biogenesis and function will also be measured (PGC-1 α , NRF-1, NRF-2, mTFA) in all subjects as done previously (98, 99). In addition, muscle will be frozen in OCT to examine if there are altered fiber type changes, and or other important markers including apoptosis (TUNEL staining).

- ii. Body Composition, Physical Function, Pain Assessments, and Physical Activity: DEXA will measure bone mineral content (BMC), bone mineral density (BMD) and body composition (fat mass, fat-free mass, and percent body fat). Pressure thresholds will be determined using an algometer during rest and after exercise. Current and usual whole body muscle pain while resting using 0-10 numeric scale. Steps, physical activity and sedentary time will be determined over a 5-day period using pedometers and accelerometers. (BodyMedia Sensewear).
- iii. Fasting Blood Draw: Glucose, insulin, total cholesterol, HDL-C, LDL-C, and triglycerides, CK, creatinine and ALT will be measured in fasting blood samples.
- iv. Insulin Sensitivity: Glucose and insulin, and insulin sensitivity will be calculated using a minimal model program following the IVGTT.
- v. Cardiovascular Function: Heart rate ECG will be measured under resting and maximal exercise conditions.

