- Telephone screen: A telephone screen will be used to collect health history, concurrent medications, and physical activity level of potential participants prior to in-person screening.

- ii. Blood draw: A screening blood draw will be used to determine presence of genetic markers associated with increased risk of myopathy from statin, creatine kinase (CK), kidney function (GFR) and liver enzymes (ALT). CK, GFR and ALT will be used to detect abnormal muscle, kidney or liver function prior to enrollment. A blood draw will be repeated at 1 month to measure for myopathy, and changes in liver and kidney function from statin use.
- iii. Intravenous glucose tolerance test (IVGTT): The subject will arrive following an overnight fast (10-12 hrs). Upon arrival, anthropometrics and vital signs will be measured. A catheter will be placed in one arm for blood draws. A fasting blood draw (~14-16mls) will be used to determine blood glucose, insulin, total cholesterol, HDL-C, LDL-C, triglycerides. Creatine kinase (CK) and liver enzymes (ALT) will be tested at 6 and 12 months during IVGTT.. CK and ALT will be used to detect abnormal myopathy, and changes in liver function from statin use for participant safety. Following the baseline draw glucose (50%) will be injected at a dose of 0.3 g/kg. Insulin will be mixed with the participant's blood for injection. Blood (5ml) and insulin (1.25 ml) will be injected into a 250 ml bag of sterile saline and mixed thoroughly. A dose of 0.025 U/kg body mass will be administered at minute 20. These mixing procedures have been safely preformed at the CTSU for a recent study (INFORM; HSC#13453).. Serial blood samples (25 total) will be obtained from the other arm at minutes 2, 3, 4, 5, 6, 8, 10, 12, 14, 16, 19, 22, 25, 30, 40, 50, 60, 70, 80, 90, 100, 120, 140, 160, and 180. Plasma will be frozen at - 80°C for later determination of glucose and insulin, and insulin sensitivity will be calculated using a minimal model program (77). A total of approximately 622 ml of blood will be collect over the 12 month intervention. After analysis for current project is complete any remaining blood samples will be stored indefinitely for future research. Fasting blood draw will be repeated at , 4 and 12 weeks. The IVGTT will be repeated at week12.

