- x. **Exercise Testing:** Whole body steady state submaximal O_2 consumption will be determined during a standard 6 min treadmill test (2.5 mph) to determine VO_2 cost. Subjects will then complete a ramped treadmill test (Bruce protocol) to determine cardiorespiratory fitness (VO_2 peak) and peak heart rate as previously

described (13). We will also investigate post exercise oxygen consumption and heart rate at 60, 90, 120, and 300 seconds after cessation of the max test to determine if exercise recovery is impacted by statins. Blood will be sampled for measurement of CK 20-30 minutes following the maximal exercise to assess potential muscle damage. Exercise testing will be repeated at week 12.

- xi. Cardiovascular Function: These measures include both heart rate and stroke volume performed under both resting and sub-maximal exercise conditions (performed on separate days). Stroke volume will be estimated by finometer placed on finger (80). Cardiovascular function will be repeated at week 12.
- xii. Physical Activity Monitoring: Physical activity levels and sedentary time will be assessed by pedometers and accelerometers (BodyMedia Sensewear) (75, 76) for 5 day periods. Physical activity monitoring will be repeated at week 12.
- xiii. Statin Therapy Intervention: Once participants have successfully completed baseline testing, the participant will be randomly assigned to 1 of 3 groups (1:1:1 ratio). Statins will be prescribed as a placebo or at a dosage of 20 or 80 mg/day (atorvastatin; Lipitor) by the study physician at KUMC, [name], MD. Subjects and research team will be blinded to the type and dose of statin. Statins will be dispensed by the KUMC Investigational Pharmacy at regular intervals during the participant's enrollment in the study. The study physician will provide care for any problems associated with the statin treatment after un-blinding by the chair of the Data Safety Monitoring Board, [name]. All doses fall within the norms of recent recommendations and are given chronically (2)

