- xiv. Aerobic Exercise Intervention: Exercise training will be performed as done previously (13) and will consist of brisk walking and/or slow jogging on a treadmill 5 d each week at approximately 65-75% of each subject's VO₂peak, 45 min/session, at an energy expenditure of 1800-2000 kcal/wk, for 12 weeks. The exercise training will follow a three-stage progression: 1. wk 1=30 min, 3 d/wk, 60% VO₂max; 2. wk 2=30 min, 5 d/wk, 60% VO₂max; and 3. wk 3-12=45 min, 5 d/wk, 60-75% VO₂peak. Exercise intensity for each session will be monitored using heart rate monitors every 5 minutes and at least four exercise sessions per week will be supervised within KUMC exercise facilities.

F. Risk/benefit assessment:

a. Potential risks:

- i. Exercise: Some risks are associated with the exercise testing used to assess maximal aerobic capacity. Cardiovascular events during maximal exercise and in recovery are possible but rare in this population (1). However, these risks could be serious. Therefore, initial screening by maximal stress test will be performed in a clinical setting under the direction of a medical monitor (medical monitor only supervises the graded exercise test). Muscle soreness and strain are possible with exercise testing and training, but these are not a serious risk. The maximal aerobic capacity test represents greater risk of cardiovascular events than the training exercise because of the increased intensity of the exercise. However, events are extremely rare, and subjects will be screened for risk of cardiovascular disease and symptoms. Emergency equipment, including defibrillator, and ambulance plan are available for all subjects. Exercise training will be monitored by trained study staff to reduce risk.

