H. Collaboration: This is a Multi-PI application from Drs. [name] and [name] from the University of Kansas Medical Center and East Carolina University, respectively. Both investigators have been conducting research on statins for several years. The project was born out of a common desire to combine their individual expertise to investigate the mechanisms underlying skeletal muscle complications associated with statin therapy in a repeated measures, longitudinal design. Due to the scope of the design (i.e., number of subjects, duration) and complexities of the primary outcome measures, it was felt a multi-PI, multi-institutional approach represented the most efficient and statistically valid means of completing the project and thereby making truly sustained impact of the field. Each investigator has trained at/frequently visited the other institute and is quite familiar with the research environments. Standard operating procedures will be developed for all common testing and primary outcome measurements, and each investigator and their key personnel will visit the other institute prior to commencing the study to conduct trial runs to insure continuity. The PIs will share responsibility for fiscal and research management. Using the multi-PI approach with two investigators with translational research experience and complimentary analytical expertise dramatically increases the power of the study and the likelihood of successfully completing the proposed aims.

I. Single IRB Review for a Multi-site study: NA

J. Personnel who will conduct the study, including:

1. Indicate, by title, who will be present during study procedure(s): PI, Study Coordinator
2. Primary responsibility for the following activities, for example:
 - a. Determining eligibility: PI, Study Coordinator
 - b. Obtaining informed consent: PI, Study Coordinator
 - c. Providing on-going information to the study sponsor and the IRB: PI, Study Coordinator
 - d. Maintaining participant's research records: PI, Study Coordinator
 - e. Completing physical examination: PI, CTSU Nurse
 - f. Taking vital signs, height, weight: CTSU Nurses
 - g. Drawing / collecting laboratory specimens: CTSU Nurses
 - h. Performing / conducting tests, procedures, interventions, questionnaires: PI, Study Coordinator
 - i. Completing study data forms: Study Coordinator
 - j. Managing study database: PI

K. Assessment of Subject Safety and Development of a Data and Safety Monitoring Plan

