- a. Key personnel:** [name], [name], [name], [name], study physician at KUMC and [name], study physician at ECU.
- b. Plan for safety monitoring and review:** [name] will serve as the Chair of the Data Safety Monitoring Board and will convene every 6 months with the other members, Drs. [name] and [name] to make decisions on safety of the participants. Enrollment data will also be reviewed twice a year by the DSMB. In addition, data will be reviewed on a yearly basis with the biostatistician, [name] to determine if the studies should be shortened due to either no measured effect or due to effects that are greater than what power calculations indicated. If problems occur with participants, blinded study staff will alert [name]. [name] will have access to dose and type of statin and will consult the study physicians cardiologist to make a decision on whether the subject should be removed from the study for safety concerns. The PI and other key personnel will be examining research data on a subject to subject basis to ensure it is accurate and to address any potential problems that may arise with the protocols. In addition, Drs. [name] and [name] will discuss data at least once per month through in person meetings or by phone to ensure that data collection is occurring in a consistent manner at both locations.**Plan for adverse event reporting:** Adverse events will be defined as any untoward medical occurrence in study participants or others immediately involved in the performance of the protocol, which does not necessarily have a causal relationship with the study treatment, but results in a change in intervention, daily function, hospitalization or rated category 3 or above using the National Cancer Institute Common Terminology Criteria for Adverse Events (CTCAE) v3.0. Expected events such as slight muscle soreness consistent with statin therapy, or those consistent with a participant's prior medical history not sufficient to alter the intervention will not be considered an AE. Staff involved in performance of the protocol (e.g. coordinators) will continually monitor participants for adverse events throughout the intervention, and study staff will assess adverse events at every testing visit as well as during regularly scheduled telephone assessments with all randomized participants.

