The PIs at both KUMC and ECU will be responsible for the quality of the data and will supervise the data acquisition with the help of study coordinators. All data will be coded for confidentiality, and only the PI, study coordinator, and study statistician will have access to the code. The results of each test on each subject will be screened by the study coordinator prior to entering on the spreadsheet. This is standard practice in our laboratories. Hard copies are kept in dedicated locked cabinets. Coded data files will be sent to the study statistician for statistical analyses. These analyses will be sent to the PI and study coordinator for dissemination to appropriate co-Is. At the end of participation in the study, each subject will receive a personal data summary of their test results. The study coordinator or a study investigator will discuss the results with the subject.

After 1 year, the PI's including the biostatistician, [name] He will be un-blinded but the study staff will remain blinded, so that the important research findings can begin to be

delineated. This will also allow for [name] to be able to examine if the trial is finding more or less significant effects for outcome measures.

- B. Sample / Specimen Collection:** All subjects will be assigned a data code. Blood and tissue samples will be labeled with the participant's data code and stored in a locked freezer. Blood and tissue samples will be stored indefinitely following completion of current project for future research.
- C. Tissue Banking Considerations:** Following completion of the current project, remaining blood and tissue samples will remain in locked freezer indefinitely. Samples will only be used by investigators of the current project, both KUMC and ECU, when a new biomarkers or techniques of interest emerge.
- D. Procedures to protect subject confidentiality:** Risks to confidentiality are reduced by assigning all subjects to a data code. Folders are stored in locked file cabinets, and only the PI and study coordinator have access to the locked files. Individual names or initials are not used in any discussions or publications of the data.

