- E. Quality Assurance / Monitoring:** Data will be reviewed twice a year by the Board Chair. In addition, data will be reviewed on a yearly basis with the biostatistician, [name] to determine if the studies should be shortened due to either no measured effect or due to effects that are greater than what power calculations indicated. The PI and other key personnel will be examining research data on a subject to subject basis to ensure it is accurate and to address any potential problems that may arise with the protocols. In addition, Drs. [name] and [name] will discuss data at least once per month through in person meetings or by phone to ensure that data collection is occurring in a consistent manner at both locations.

V. Data Analysis and Reporting

- A. Statistical and Data Analysis:** This project is a two-factor study. One factor is treatment group (between subjects) and a second factor is time of data collection (0, 1, 6, and 12 months) (within subject). The data analysis will be carried out for the primary outcome variable of cardiorespiratory fitness, in addition to other outcome variables (muscle mitochondrial change, and insulin sensitivity, etc.). For each measure, its baseline measure and age will be added as covariates to adjust for the individual difference at baseline. Two-way interaction between treatment and time will be added in the model for testing if the outcome changes differently between groups over time. Additional variables, such as demographics, BMI, physical activity, etc. may also be included as covariates. If the test of trend difference is significant, then the comparison at each time point will also be considered to identify when the difference between groups reaches the maximum. Least Square Means will be used for the aforementioned comparisons. The statistical analysis will be performed with mixed procedure in STATA 13.1 (StataCorp LP, College Station, TX). Mixed model does

not require complete data for a longitudinal study. Residual analyses will be conducted and efforts to address those will be made, including appropriate transformations.

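### Staff who conduct the tests also review each participant's results, and nothing keeps week-4 LDL-C from them before the week-12 VO2peak test

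*Combined protocol and SAP*

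**What the plan says.** Section II.B calls the study double-blinded, and section II.E.a.xiii says: "Subjects and research team will be blinded to the type and dose of statin".

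The measurements:
- Section II.A.b.iii: "Glucose, insulin, total cholesterol, HDL-C, LDL-C, and triglycerides, CK, creatinine and ALT will be measured in fasting blood samples".
- Section II.E.a.iii, on timing: "Fasting blood draw will be repeated at , 4 and 12 weeks". (The gap before the 4 is in the text.)
- Section II.E.a.x repeats exercise testing, including VO2peak, at week 12.

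The people:
- Section IV.A, on data entry: "The results of each test on each subject will be screened by the study coordinator prior to entering on the spreadsheet".
- Sections II.K.b and IV.E: "The PI and other key personnel will be examining research data on a subject to subject basis to ensure it is accurate".
- Section II.J: "Performing / conducting tests, procedures, interventions, questionnaires: PI, Study Coordinator".
- Section II.F.a.i, on training: "Exercise training will be monitored by trained study staff to reduce risk".

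Section IV.A also provides for unblinding after 1 year. The sentence is garbled, but it appears to cover the PIs and the biostatistician, with study staff remaining blinded. No section withholds, delays or batches lipid results, and none names a separate assessor for VO2peak.

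**The concern.** Section I.B describes statins as highly effective at lowering LDL-C. A week-4 LDL-C read beside the baseline value therefore carries information about allocation, and the roles that see it are the roles that run the tests.

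VO2peak, treadmill time, strength and pain ratings depend on effort and can respond to encouragement. Sections II.A.a.i and II.E.a.x give no criterion for ending a peak test or accepting it as maximal. The investigators also state in section V.B which arms they expect to improve. Knowledge of treatment, even if imperfect, could influence the remaining eight weeks of training or the conduct of the week-12 test. Such an influence could not be reliably removed in the analysis.

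**Working it through.** The plan states no figure on this point. The check has three parts.

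**1. Is there a path from allocation to tester?**
- LDL-C is in the fasting panel (II.A.b.iii, II.E.a.iii).
- The fasting draw is repeated at week 4, and VO2peak is tested at week 12 (II.E.a.iii, II.E.a.x): 12 − 4 = 8 weeks.
- The coordinator screens all results and the PI reviews by subject (IV.A, II.K.b, IV.E).
- The same two roles perform tests and interventions (II.J).
- No rule blocks the path. Section II.E.a.iii describes freezing plasma for later determination only for glucose and insulin, not for lipids.

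The path is open. Whether it is used depends on when lipids are returned, which is not stated.

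**2. How informative would LDL-C be?** The documents give neither the LDL-C response nor its variability. Assumptions:
- statin and placebo differ by D = 20 to 50 percentage points in change from baseline;
- one LDL-C measurement has a within-person SD of s = 10 to 15%.

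Staff compare two measurements, so the SD of the change is √2 × s: √2 × 10 = 14.1 and √2 × 15 = 21.2. With a cut midway between the two means, the proportion classified correctly in each group is p = Φ(D / (2 × √2 × s)).

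| D | s | SD of change | D / (2 × SD) | p |
|---|---|---|---|---|
| 20 | 15 | 21.2 | 0.47 | 0.68 |
| 30 | 10 | 14.1 | 1.06 | 0.86 |
| 50 | 10 | 14.1 | 1.77 | 0.96 |

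Variation in drug response and adherence is not included and would lower p. Exercise can itself lower LDL-C (I.C), but all arms train, so this mainly adds noise.

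**3. Which comparisons are exposed?** Let f0, f20 and f80 be the proportions of placebo, 20 mg and 80 mg participants whom staff take to be on a statin. Let δ be the average VO2peak change caused by being so regarded. The bias in each contrast is then:
- 80 mg versus placebo: (f80 − f0) × δ
- 20 mg versus placebo: (f20 − f0) × δ
- 80 mg versus 20 mg: (f80 − f20) × δ

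If both doses lower LDL-C by the same D, then f20 = f80 = p and f0 = 1 − p. Each placebo contrast is shifted by (2p − 1) × δ, which is 0.36δ at p = 0.68 and 0.92δ at p = 0.96. The dose contrast is not shifted. If 80 mg lowers LDL-C more than 20 mg, a smaller shift of (f80 − f20) × δ remains there. The documents give no basis for δ, so no shift in ml/kg/min can be stated.

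**The case against.** The strongest reply is that early viewing is an inference. Section IV.A requires screening before data entry, which could fall after week 12, and section II.E.a.ii gives only safety purposes for the 1-month draw. This stands: the documents show that allocation can be inferred, not that it will be.

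The roles are also less clear-cut than they look. Trained study staff monitor training, and a medical monitor supervises the graded exercise test (II.F.a.i). Section II.J lists titles, so the person who screens a result need not test that participant. Training follows a fixed progression with heart-rate checks (II.E.a.xiv), and RQ and heart rate are recorded at each treadmill stage (II.A.a.i). These points limit discretion but do not remove it, because section II.J still assigns tests and interventions to the PI and coordinator.

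Three stronger readings are tempting and are not supported:
- **Bias always favours the hypothesis.** Sections II.C and V.B expect 20 mg to behave like placebo and only 80 mg to be blunted. Staff who can infer only that a participant takes a statin cannot separate the arm expected to do well from the one expected to do badly. Treating both alike would push 80 mg versus placebo toward the hypothesis, but 20 mg versus placebo away from the expected similarity.
- **LDL-C is close to an allocation label.** Using the SD of a single measurement gives Φ(20/30) = 0.75 to Φ(50/20) = 0.99, but the comparison with baseline is a change score, so that SD is too small.
- **A particular VO2peak bias or type I error follows.** Any such number rests on an assumed δ.

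Nor is the code mentioned in section IV.A evidence of unblinding: it is the subject data code. Participants receive their lipid profile only at the end of participation (V.C), so the point concerns staff.

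**Conclusion.** The point holds as a gap in protecting the blind. The stated duties let staff who conduct effort-dependent tests see week-4 LDL-C, and no rule prevents it. If results are returned before week 12, those staff could classify statin versus placebo correctly in roughly 68% to 96% of participants, under the assumed 20 to 50% fall and 10 to 15% within-person SD.

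The contrasts mainly exposed are the powered comparison of 80 mg with placebo and the exploratory non-inferiority check of 20 mg against placebo. The powered comparison of 20 mg with 80 mg is less affected. The direction of any bias is plausible but not certain, and its size in VO2peak is unquantified. The documents do not show that the blind has been or will be broken. They leave open a route that is easy to close beforehand and hard to correct afterwards.

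**What to change.** Amend sections IV.A and IV.E, and the matching sentence in II.K.b, as follows:

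- Post-randomisation lipid results are held by the laboratory or sent only to a role that is already unblinded, such as the DSMB chair.
- These results are excluded from coordinator screening and from PI and key-personnel subject-level review until that participant's week-12 tests are complete, preferably until database lock. Under the database-lock option, the lipid part of the personal summary in V.C would have to follow later or come from someone not involved in testing.
- CK, ALT and kidney safety reporting is unchanged. The enzyme-based withdrawal provision in II.D.b uses CK and ALT, so no stated safety check is lost.
- Anyone unblinded under the 1-year provision in IV.A does not conduct or supervise VO2peak tests of later participants. Withholding lipids alone would not cover this route.

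If the laboratory already batches lipids until after week 12, a sentence saying so would close the lipid route. The cost is a reporting instruction to the laboratory, a few sentences of protocol text, and later entry and checking of lipid data. The 1-year restriction may also require another tester where a PI would otherwise have done the test.

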B. Study Type and Design: This study is a longitudinal, repeated measures, double-blinded design with subjects randomly assigned to placebo, low (20 mg/d) or high (80 mg/d) atorvastatin therapy during a 12-week aerobic exercise training protocol. We expect to screen approximately 150 participants to enroll (randomize) a maximum of 80 participants. The overall goal is to have 60 participants complete all study procedures (20 in each group). Repeated measures design allows each subject to serve as their own control. Placebo groups are included to account for potential changes in muscle mitochondrial function independent of statin therapy over the 1 year dose-response.

C. Sample size, statistical methods, and power calculation: The randomization for study drugs will be carried out by the biostatistician using a computer-based random number generator at a 1:1:1 allocation. Sample size for the study is powered on the basis of detecting a difference in VO₂peak between the EX+Plac group and the EX+Atorva80 group as well as between the EX+Atorva20 group and the EX+Atorva80 group at 12 weeks post-treatment. In our previously published study(13) (Table 2) the EX only group had a mean 2.6 ml/kg/min increase in VO₂peak following 12 weeks of training while the EX+Statin group only had a 0.4 ml/kg/min increase in VO₂peak. The estimated effect size of between group differences is 0.9 (Cohen's d). The increase of VO₂peak in the EX+Atorva20 group is expected

to be similar to that of EX+Plac group. A sample size of 35 per group provides 80% of power of detecting an effect size of 0.75 for a two-sided, two-sample t-test at 0.025 levels. Here, we use 0.025 for each group comparison to maintain the overall type I error rate at 0.05 level using Bonferroni correction. Assuming variances similar to what was observed in the pilot study, this study is powered to detect a difference of 1.53 ml/kg/min VO₂peak between groups. These power calculations led to a desired final sample size of 105 (35/group). We plan an enrollment of 120 (40/group) subjects to account for 10% dropout rate. The subject enrollment will be split equally between the two sites. As an exploratory analysis, the mean difference of VO₂peak (EX+ Atorva20- EX+ placebo) and its 95% confidence interval (CI) will be estimated. If the lower bound of the 95% confidence interval is greater than -0.8 ml/kg/min, EX+ Atorva20 will be considered non-inferior to EX+ placebo.

D. Subject Criteria

[figure not shown]

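### Section IV.A, on its natural reading, unblinds the PIs after 1 year for an efficacy reason, against the open-ended blind in II.B and II.E; week-12 tests or data decisions outstanding then would lose investigator blinding

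*Combined protocol and SAP*

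**What the plan says.** **The blind.** Section II.B states: "This study is a longitudinal, repeated measures, double-blinded design". Section II.E.a.xiii adds: "Subjects and research team will be blinded to the type and dose of statin". Neither makes an exception for the PIs or says when the blind ends.

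**The unblinding.** Section IV.A, Data Management and Security, states: "After 1 year, the PI's including the biostatistician, [name] He will be un-blinded but the study staff will remain blinded". The purpose given is that work on the main findings can start. The next sentence adds that a named person can then see whether outcome effects are turning out more or less significant.

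**What the PIs do.** Section II.J assigns testing as follows: "Performing / conducting tests, procedures, interventions, questionnaires: PI, Study Coordinator". It also gives the PI the database. Section IV.A has the PIs at both institutions supervise data acquisition, and sends statistical analyses to the PI and coordinator without saying whether these are split by arm. Sections II.K.b and IV.E have the PI check data subject by subject. Section V.B records the expectation that the 80 mg arm will adapt less than the other two.

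**Other unblinding.** Safety has its own routes: the DSMB chair (II.E.a.xiii), a person with access to dose and type of statin (II.K.b), and an unblinded investigator who assesses adverse events (adverse event plan in II.K).

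**The concern.** A reader of sections II.B and II.E would take it that nobody who tests participants or handles outcome data knows the arms until the trial is over. A reader of section IV.A would conclude that the PIs do know from some point on, and for a reason unrelated to any participant's safety.

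The primary outcome makes this matter. VO2peak is measured by gas exchange, but a maximal treadmill test also depends on encouragement and on when it is stopped, and queries on outlying values call for judgement. A PI who knows assignments and expects one arm to do worse could shift later results without meaning to. A PI who knows only results by arm could still be influenced in choices that section V.A leaves open, such as optional covariates and transformations. No section takes an unblinded PI off these tasks.

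**Working it through.** The plan gives no figure to reproduce here, so the check is a comparison of sections followed by an illustration of exposure.

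**1. Who is unblinded.** The subject of the section IV.A sentence is plural, and the sentence sets those people against the study staff, who stay blinded. The odd fragment in the middle looks like a partly removed personal name. On that basis the PIs and the biostatistician are both unblinded. That only the biostatistician is meant is possible, but fits the plural and the contrast poorly.

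**2. Why.** The stated purpose concerns findings and significance. The safety routes in II.E.a.xiii and II.K do not depend on this sentence.

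**3. Whether the trial is still running.** Findings are only to be started on, staff remain blinded, and section IV.E has a yearly review of whether to shorten the studies. This implies an ongoing trial but does not state it.

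**4. When.** The year has no stated origin. Participation lasts 12 weeks (II.E), yet 12-month wording survives elsewhere: "over the 1 year dose-response" in II.B, "over the 12 month intervention" in II.E.a.iii, strength testing at 1, 6 and 12 months in II.E.a.vii, and "time of data collection (0, 1, 6, and 12 months" in V.A. The 1-year mark may have been carried over in the same way.

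**5. Which VO2peak tests could be exposed.** Randomisation follows baseline testing (II.E.a.xiii) and exercise testing is repeated at week 12 (II.E.a.x). Only the week-12 test could be affected.

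**6. Share of week-12 tests after unblinding.** Assumptions: the year runs from first randomisation, and participants are randomised uniformly over A months. The documents give neither.

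- 12 weeks = 84 days; 84 / 30.44 = 2.76 months.
- A test falls after month 12 if the participant was randomised after month 12 − 2.76 = 9.24.
- Share = max(0, (A − 9.24) / A).
- A = 9: 0%.
- A = 12: 2.76 / 12 = 23%.
- A = 18: 8.76 / 18 = 49%.
- A = 24: 14.76 / 24 = 61%.

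Rounding 12 weeks to 3 months gives 0%, 25%, 50% and 62.5%. The share does not depend on the enrolment total.

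**7. What these shares do and do not cover.** They count all week-12 tests. The share run by an unblinded PI is lower, because testing is shared with the coordinator. Data decisions are not bounded in this way: review is subject by subject, so a PI unblinded before lock could still rule on data from tests already done. If the year instead runs from each participant's own start, that participant's week-12 test is about 52 − 12 = 40 weeks past, so no one's own test is exposed. The PIs could nevertheless learn assignments or results by arm while others were still in the study.

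**The case against.** The strongest reply is that there is no contradiction, only a general rule and a dated exception. The protocol already makes exceptions for safety, section IV.A keeps staff blinded, and nothing unblinds participants. Part of this stands: the two statements could coexist if the protocol said so. It does not. Sections II.B and II.E mention no later exception, and section IV.A puts no limit on what an unblinded PI may do.

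The second reply is that exposure may be nil, because the sentence is garbled, the year has no anchor and the wording may be left over. This also stands, and it rules out any claim that results will be biased. It does not rescue the sentence, which needs rewriting under every reading.

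The third reply is that other safeguards limit the damage: a fixed Bruce protocol, standard operating procedures for primary outcome measurements (II.H), coordinator screening of each result before entry (IV.A), and blinded participants and staff. These make any bias probably small.

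A reader might infer three stronger points that the documents do not support:

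- **An inflated type I error of some stated size.** This would need a bias per affected test and the share of tests affected. The documents give neither, so any such figure would only reflect the chosen inputs.
- **That the yearly review plainly has no use for this unblinding.** Section II.C says "The randomization for study drugs will be carried out by the biostatistician", but producing the sequence does not establish access to assignments during analysis. Section IV.A itself lists the biostatistician among those to be unblinded later.
- **That the PI and coordinator already hold the treatment code.** Section IV.A describes that code as a confidentiality measure.

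**Conclusion.** The concern holds as an unreconciled conflict over a core safeguard. As written, section IV.A permits PI unblinding for efficacy reasons that sections II.B and II.E.a.xiii exclude, and nothing separates the PIs from outcome testing or data decisions afterwards. Any such work outstanding at that point would lose investigator blinding.

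The amount of such work is unknown. It could be none. Under the two assumptions in the working it ranges from no week-12 tests for 9 months' accrual to 61% for 24 months. These are shares of tests, not measures of bias, and no effect on the error rate or on the treatment difference is claimed. It is also unstated whether the PIs would see individual assignments or only results by arm.

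This should be fixed. The case rests on the conflict and the low cost of removing it, not on demonstrated harm. Confidence is medium, because the natural reading of one damaged sentence carries much of the weight.

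**What to change.** Replace the section IV.A sentence with:

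> Only the biostatistician is unblinded for the yearly review. The PIs and all personnel who train, test, or review or query outcome data remain blinded to assignments and to results by arm until the last week-12 test is done and the database is locked.

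State in the same section that analyses sent to the PI and coordinator before lock are pooled over arms.

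Leave the safety unblinding routes in II.E.a.xiii and II.K as they are. A cross-reference to them would keep the new sentence from being read as cancelling them.

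The cost is two text edits in one section. The downside is that the PIs wait until database lock to see results by arm. Whether the DSMB should receive comparative results is a separate decision that this point does not require.
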